3.2 Secondary endpoints

Secondary objectives are assessed with the adverse treatment outcomes defined above (relapse, default, failure and death).

Genetic and laboratory predictors of TB treatment outcome are described in section 5.4, while secondary and tertiary analyses are defined in 8.3.4.

4. SUBJECTS, POPULATION & SELECTION

4.1 Settings, selection & recruitment

The study will take place in eight DF Bangladesh outpatient clinics with an LED TB fluorescence microscopy laboratory (Sarishabari, Madhupur, Bhaluka, Fulbaria, Iswarganj, Netrakona, Purbodhola, Kendua), shown on the map in Annex III. These clinics are located in the Greater Mymensingh district and have been selected because of their proximity to the three DF hospitals with a reference laboratory capable of doing rapid DST and toxicity monitoring. Five of them are also the oldest project clinics, where drug resistance surveillance was started already in 1995. The proposed study would have the additional benefit of adding a fifth drug resistance monitoring data point without extra cost, since *rpoB* sequencing on preserved sputum from all enrolled cases will be performed to provide the denominators for some study endpoints and to define cases with acquired resistance. Together, these clinics register about 2000 TB cases per year. They have in general advanced disease, but there is practically no HIV and also MDR prevalence is low (1-2% of new cases).

Patients presenting with symptoms suspect for TB as defined by the NTP (mainly cough for at least 3 weeks) will be tested as per standard guidelines, i.e. 2 sputum smears for AFB, which can be repeated at 2 weeks intervals in case the suspicion remains and previous tests are negative. Additionally chest X-Ray is used to diagnose smear-negative pulmonary TB. Other suspects (extra-pulmonary) are referred to Medical Officers for appropriate investigations. Standard AFB-smears will in principle be done using FM technique, which can be temporarily replaced by ZN in case of

equipment breakdown. One sputum smear with at least one AFB detected is sufficient to register a case, or a decision by a Medical Officer based on clinical and other examinations.

Once patients are registered and comply with the exclusion / inclusion criteria that are checked per routine, written informed consent will be asked. Consenting patients will be further assessed for eligibility, and if all in- and exclusion criteria are fulfilled, they will be enrolled and randomized over the 2 treatment arms. Patients refusing will all be put on the standard regimens.

4.2 Inclusion and exclusion criteria

In order to be eligible, study participants **must meet the following criteria**:

- Diagnosed with smear-positive pulmonary TB
- 15 years or older
- Able and willing to provide written informed consent

Potential participants meeting any of the following criteria **will not be enrolled in the study**:

- contacts of MDR-TB patients and other MDR-TB suspects diagnosed with resistance on rapid DST for rifampicin performed prior to start of treatment according to NTP guidelines
- smear-negative pulmonary and extra-pulmonary TB cases
- patients in need of hospitalization because of very bad general condition or complications
- patients with clinically active liver disease, for the study defined as jaundice confirmed by a local Medical Officer (Government)
- any known HIV-positive patient (although none are expected)
- any patient with known hepatitis B or C infection
- pregnant women; in addition, patients in the intervention arm who become pregnant during treatment will be switched to the control arm

4.3 Sample size

The sample size selected is 1000 patients (500 randomized to intervention, 500 to control). The study will be conducted in eight DF Bangladesh outpatient clinics with an LED TB fluorescence microscopy laboratory that register about 2000 TB cases per year of which 65% are smear-positive pulmonary TB (new or retreatment). Enrolment will target 1000 randomised smear-positive pulmonary TB patients. Given an expected 5% refusal rate, it is expected that recruitment will require 9-10 months.

4.4 Randomization

Two randomization lists will be prepared at ITM prior to study start: one for new cases, one for retreatment cases. To ensure (approximate) treatment balance within study sites, the randomization list will be blocked. Treatment allocation will be concealed until the completion of the screening procedures and the final recruitment of the patient using sealed envelopes labelled with the randomization number and containing the treatment group allocation.

4.5 Withdrawal and termination of the study

Reasons for Withdrawal

Subjects may be withdrawn from the study if:

- The subject or legally acceptable representative withdraws the consent
- The Investigator judges that further participation would have negative effects on the subject's health. In this case, the study team will follow the patient up to resolution of such negative event.

Handling of Withdrawals

Patients withdrawn from study participation will continue to receive standard care, as required by their condition. This includes continuation of the best possible TB treatment as long as needed, and also care of any adverse events or complications that may or may not be due to the study procedures. The principal investigator will be responsible to assure that this care is provided, either at DF clinics or hospitals, either by referral to specialists at nearby Medical Colleges or other providers.

Loss to follow-up during treatment is defined by the default outcome definition, i.e. 2 months treatment interruption. As per standard NTP guidelines patients will be contacted by phone or have a home visit performed if they are late for an appointment.

Loss to follow-up for relapse assessment will be considered separately. These patients will be invited to attend 12 months after cure or default, also complemented by phone convocations and home visits as required.

Termination of Study

If the study is prematurely terminated or suspended, the Sponsor will promptly inform the investigators/institutions, and the regulatory authority(ies) of the termination or suspension and the reason(s) for the termination or suspension. The EC's will also be informed promptly and provided the reason(s) for the termination or suspension by the Sponsor or by the investigator/institution, as specified by the applicable regulatory requirement(s).

5. STUDY PROCEDURES

5.1 Study/visit schedule

SCHEDULE OF ASSESSMENTS

	Screening	Enrollment (V0)	Week 1 (V1)	Week 2 (V2)	Week 4 (V3)	Month 2 (V4)	Month 3 (V5)	Month 4 (V6)	Month 5 (V7)	Month 6 or 8 (V8)	Month +12 ⁴ (V9)
Medical history		X									
Informed Consent		X									
Clinical examination	X	X		X	X	X	X	X	X	X	X
Weight		X		X	X	X	X	X	X	X	
Temperature		X		X	X	X	X	X	X	X	
Sputum sample for AFB smear (ZN or FM)	X	X ²	X ²	X ²		X	X (if 2M+)		X	X	X ⁵
Sputum sample for FDA vital staining		X ²	X ²	X ²			X ³		X ³	X ³	
DST referral	X ¹			X ²			X ³		X ³	X ³	
Treatment		X	X	X	X	X	X	X	X	X	
Pregnancy test (urine)		X ⁶									
Biochemistry (liver tests)		X		X	X	X					
Adverse Event collection				X	X	X	X	X	X	X	
Outcome assessment									X	X	X

¹ Contacts of MDR-TB or retreatment cases only, if smear-positive

² - Intervention arm: DST referral only if responding to the 2-weeks screening criteria described in the protocol

- Control arm: DST referral if still fever (temperature $\geq 38^{\circ}\text{C}$)

³ If smear-positive at this time = standard indication of the NTP, controls as well as intervention arm

⁴ This is the follow-up visit 12 months after end of treatment

⁵ And for culture: this is the only time the specimens will always be used for microscopy and culture

⁶ Women of childbearing age only

Controls will be treated as per NTP guidelines, but will additionally be monitored for transaminase increase and toxic hepatitis, as will be those of the intervention arm (see further).

Patients in the intervention arm will receive high-dose rifampicin Cat. 1 regimen and will also be screened earlier for delayed conversion of sputum smears for TB bacilli and rifampicin resistance, as shown in the algorithm in Annex 2. If retreatment is needed for the intervention arm, they will be started or re-started on the high-dose Cat. 1 regimen as long as they are not shown to be rifampicin resistant.

Once rifampicin resistance is detected, patients (intervention, controls or non-consenting) will be put on the MDR regimen.

All surviving patients who can be retrieved will be checked for relapse by smear and culture for TB 12 months after the end of treatment.

The outcome of pregnancy occurring during treatment and the baby's health will be recorded for both treatment arms.

5.2 Obtaining informed consent

The informed consent procedure will describe the purpose of the study, the procedures to be followed, the risks and benefits of participation, etc. If a subject (or parent or guardian) is unable to read or write, a signature from a witness to the informed consent discussion will be obtained. Subjects (or parents or guardians) will be informed that participation in the study is completely voluntary and that the participant can withdraw from the study at any time without any negative consequences.

All patients will be asked to give their informed consent to participate in the study, before undergoing any study-specific procedures. The Informed Consent Form (ICF) as well as the informed consent interview will describe the purpose of the study, the procedures to be followed, the risks and benefits of participation, the voluntary nature etc., as described in the E6 ICH GCP Guidelines.

The interviews will be conducted in the native language of the patients by a qualified person formally identified by the Investigator. Written information and consent forms in the local language will be provided to the patients or legally authorized representatives for their review. The written information and consent form is currently written in English, but it will be further translated in Bengali, and back to English for the accuracy of proper translation, with certification after verifying the original and back-translated copy.

Individuals potentially eligible for the study (i.e. individuals diagnosed with smear-positive pulmonary TB) will be informed on the modalities of TB treatment and on the possibility to participate in the study by the clinic's TB/Leprosy Control Assistants (TLCA) routinely in charge of diagnosis and treatment. Additional information on the eligibility criteria will be obtained (e.g. age) if missing in the patient file. Once eligibility has been confirmed, TLCAs will ask if the potential participant is ready to decide whether or not to join the trial. Patients must be given enough time to ask questions and to take a free decision (including a time frame of a few days to discuss their participation with family members). If the individual is willing to participate, he/she will be given the ICF and the content will be read by the TLCA. Once checked the ICF is understood, the TLCA will invite the participant to sign the form, add his/her name (or thumb-printing whenever they are illiterate) and countersign it.

If the patient is minor of age/not emancipated, the consent must be given by a parent or legal guardian according to national law; however, in this case, the investigator is responsible to check that the patient him/herself is also freely willing to take part in the study by means of giving informed and written assent.

If a patient (or guardian, if applicable) is unable to read or write, an independent witness must be present during the informed consent interview and the signature of the independent witness will be obtained, in addition to the patients' thumbprint. For adult individuals incapable of providing

informed consent for other reasons (e.g. mentally disabled), consent is obtained from a legally authorized representative in accordance with applicable law.

5.3 Specific procedures and activities

- Screening visit:
 - o Clinical symptoms and signs of TB to select suspects for AFB-smear; refer to Medical Officer if not a suspect
 - o Spot sputum collected for AFB if responding to TB suspect criteria; request for a second early-morning sputum next day
 - If AFB positive and patient does not respond to MDR suspect criteria: proceed with V0 procedures (same day if possible)
 - If positive and patient responds to MDR suspect criteria (MDR contact or retreatment case): referral for DST, treatment depending on rapid result
 - MDR regimen if rifampicin resistant; not eligible for the study
 - if susceptible or no result: eligible, continue with V0
- Enrolment visit V0:
 - o Always clinical symptoms and signs, medical history, weight, temperature, patient information on standard TB treatment and DOT arrangements
 - Medical history: previous TB treatment; concomitant disease such as diabetes and HIV
 - o Signs and symptoms: check for vital signs, severe anemia, dyspnea, chest pain, suspect of TB complications: refer if severely ill or complications suspected. Responding to exclusion criteria: register as non-study and start standard TB treatment or refer (active liver disease, patients to be hospitalized...)
 - o No exclusion: explain study, ask informed consent
 - Refused: register as non-study and start standard TB treatment
 - Accepted: perform study specific procedures
 - Perform urinary pregnancy test for all women of childbearing age not aware that they are pregnant. If the test is positive, do not include in the study but register as non-study patient and start on standard TB treatment.
 - Pregnancy excluded: liver test, register as study patient and randomise to intervention or control arm
 - **Intervention only:** quantified auramine and FDA smears; start high-dose Cat. 1
 - Control arm: start Cat. 1 or Cat. 2 depending on history
- Visit after one week V1: **intervention patients only**
 - o Give treatment, record attendance
 - o Sputum for quantified AFB smears (auramine and FDA)
 - o Stop all drugs and refer in case of hepatitis suspicion (feeling sick, anorexia, vomiting, jaundice)
- Visit after two weeks V2: Intervention + control arm
 - o Clinical check, weight, temperature: improving signs and symptoms of TB?
 - o Give treatment, record attendance
 - o Liver test
 - o **Intervention arm only:** Sputum for quantified AFB smears (auramine and FDA), apply algorithm
 - refer for rapid DST if indicated by algorithm; switch to MDR if rifampicin resistant
 - otherwise continue high-dose treatment
 - o **Control arm only:**

- refer for rapid DST if still fever (temperature $\geq 38^{\circ}\text{C}$); switch to MDR if rifampicin resistant
 - Enquire, register adverse effects. Stop all drugs and refer in case of hepatitis suspicion (feeling sick, anorexia, vomiting, jaundice)
- Visit after four weeks V3: intervention + control arm
 - Clinical check, weight, temperature: improved signs and symptoms of TB?
 - Give treatment, record attendance
 - Liver test
 - Enquire, register adverse effects. Stop all drugs and refer in case of hepatitis suspicion (feeling sick, anorexia, vomiting, jaundice)
- Visit after 2 months V4: intervention + control arm
 - Clinical check, weight, temperature: signs and symptoms of TB absent?
 - Give treatment, record attendance
 - Cat. 1: sputum smear for AFB
 - Refer for rapid DST if AFB-positive (auramine and FDA) and clinically poor evolution; switch to MDR treatment if rifampicin resistant
 - Liver test
 - Enquire, register adverse effects. Stop all drugs and refer in case of hepatitis suspicion (feeling sick, anorexia, vomiting, jaundice)
- Visit after 3 months V5: intervention + control arm
 - Clinical check, weight, temperature: signs and symptoms of TB absent?
 - Give treatment, record attendance
 - Sputum smear for AFB: all Cat. 2 and Cat. 1 patients positive at month 2
 - Refer for rapid DST if AFB-positive (auramine and FDA); switch to MDR treatment if rifampicin resistant
 - Enquire, register adverse effects. Stop all drugs and refer in case of hepatitis suspicion (feeling sick, anorexia, vomiting, jaundice)
- Visit after 4 months V6: intervention + control arm
 - Clinical check, weight, temperature: signs and symptoms of TB absent?
 - Give treatment, record attendance
 - Sputum smear for AFB: Cat. 2 positive at month 3 only
 - Refer for rapid DST if AFB-positive; switch to MDR treatment if rifampicin resistant
 - Enquire, register adverse effects. Stop all drugs and refer in case of hepatitis suspicion (feeling sick, anorexia, vomiting, jaundice)
- Visit after 5 months V7: intervention + control arm
 - Clinical check, weight, temperature: signs and symptoms of TB absent?
 - Give treatment, record attendance
 - Sputum smear for AFB: all patients
 - Declare failure if positive and refer for rapid DST if AFB-positive
 - Switch to MDR treatment if rifampicin resistant
 - Rifampicin sensitive:
 - Control arm: start Cat. 2
 - Intervention: re-start Cat. 1
 - Enquire, register adverse effects. Stop all drugs and refer in case of hepatitis suspicion (feeling sick, anorexia, vomiting, jaundice)
- Visit after 6 months (or 8 months for Cat. 2) V8: intervention + control arm
 - Clinical check, weight, temperature: signs and symptoms of TB absent?
 - Stop treatment, record attendance
 - Sputum smear for AFB: all patients
 - Declare cured if negative and inform about signs of relapse
 - Declare failure if positive and refer for rapid DST if AFB-positive

- Switch to MDR treatment if rifampicin resistant
- Rifampicin sensitive:
 - Control arm: re-register, start Cat. 2
 - Intervention: re-register, re-start Cat. 1
- Enquire, register adverse effects
- Make appointment for check-up after 12 months

- Visit 12 months after end of treatment V9 (intervention + control arm cured or defaulted)

- Reminders, home visit if not attending
- History from relatives / neighbours if not met (retreated or died of TB?)
- Clinical check: signs and symptoms of TB absent?
- If attending at the clinic only: weight, temperature
- Sputum smear and culture for AFB
 - If negative: further passive follow-up
 - If positive: declare relapse and refer for rapid DST
 - Switch to MDR treatment if rifampicin resistant
 - Rifampicin sensitive:
 - Control arm: re-register, start Cat. 2
 - Intervention: re-register, re-start Cat. 1

All enrolled patients will be monitored intensively for drug toxicity (clinical; liver enzymes during the first 2 months). Treatment will be interrupted in case of a serious adverse event, possibly due to the TB drugs, and patients referred to the nearest project hospital. In case of toxic hepatitis, after full recovery drugs will be re-introduced in hospital one by one, aiming at re-starting the same regimen since this toxicity is often transient and probably not rifampicin dose-related.

Unscheduled visits can take place at any time during the patients participation in the study. During these visits, all study procedures will be performed if needed, and data will be collected.

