TREATMENT	
Intervention: 2HREZ/4HR Cat. 1, modified by using double dose rifampicin throughout. This will apply to new as well as retreatment cases
 
Controls: the standard program treatment. This consists for new cases of 6 months of rifampicin and isoniazid, complemented by ethambutol and pyrazinamide during the first 2 months (Cat. 1, 2HREZ/4HR); for retreatment cases, streptomycin is added during the first two months, pyrazinamide is added during the first three, and ethambutol throughout, prolonging to a total of 8 months (Cat. 2, 2SHREZ/1HREZ/5HRE)

FOLLOW-UP	
Sputum smears for acid-fast bacilli at 2-3, 5 and 6 months (3-4, 5 and 8 for Cat. 2). Referral of positives for rapid rifampicin DST from 2nd or 3rd month onwards.
 
Additional routine plus vital staining smears after 1 and 2 weeks for the intervention only, with referral for rapid DST if the number of bacilli has not declined by at least one log by 2 weeks; referral for rapid DST in the control arm based on fever still present at 2 weeks. Prompt switch to specific MDR regimen if resistance is detected.

ANALYTICAL METHODS	
Analyses are planned at the end of the primary treatment period (interim analysis) and after 1 year post-treatment follow-up (final analysis).
 
Primary Analysis: Counts and proportions (and 95% confidence intervals) of patients with any adverse treatment outcome, and by adverse treatment outcome category, will be presented. Odds ratio's (ORs) and 95% CIs will be estimated from a logistic regression model with effects for arm (intervention vs control), clinic, and stratum (new/re-treatment case). Similar analyses will be performed for the primary safety endpoint.

SAFETY	
Clinical monitoring at each follow-up visit, with referral to Medical Officers or project hospitals as per standard guidelines. Additionally, both arms will be screened for liver toxicity biochemically at 0, 2, 4 and 8 weeks of treatment. Treatments will be interrupted if transaminase increase to >5 ULN, with referral for hospitalization.

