We expect that the standard pulmonary TB treatment regimens recommended by the Union² can be optimized by using daily high dose rifampicin during Cat. 1 primo-treatment. For the here proposed pilot study, dosing of rifampicin would be doubled, while standard dose isoniazid, pyrazinamide and ethambutol would be maintained. Management decisions would be made after 2 weeks of intensive phase, based on remaining numbers and decline of TB bacilli on microscopy for AFB [auramine and fluorescein diacetate (FDA) vital staining]. Those with min. 1 log decline in the number of AFB by FDA smear, or already negative, would continue the unaltered regimen. Those not meeting these criteria would be referred for rapid DST by slide DST and/or Xpert MTB/RIF, depending on ease of referral. In case no rifampicin resistance is detected they would continue the optimized Cat. 1 treatment, with further monitoring by smear and rapid DST as per National TB Programme (NTP) indications, i.e. rapid DST in case a smear is positive at 3, 5 or 6 months; those diagnosed with rifampicin resistance at any time and by any technique would be switched immediately to the standard short "Bangladesh" MDR-TB treatment regimen. In the control arm, referral for rapid DST would be based on non-remittance of fever at the end of the second week, otherwise treatment management remains the same. Failures, relapses and other recurrences of the first-line regimen would all undergo rapid DST, and if not found to be rifampicin resistant they would be re-started on the same 6-month Cat. 1. The current Cat. 2 first-line retreatment regimen would no longer be used in the intervention arm.

Intervention and control treatment regimens (Rh: double dose rifampicin)

New cases	
- intervention:	2 HRhZE / 4 HRh
- control:	2 HRZE / 4 HR (Cat. 1 regimen)
Retreatment cases	
- intervention:	2 HRhZE / 4 HRh
- control:	2 SHRZE / 1HRZE / 5 HRE (Cat. 2 regimen)
MDR patients detected at any time	
	4 KHPtoGCEZ / 5 GCEZ (MDR regimen)

The expected benefits from this optimized treatment regimen cascade are:

1. Reduced occurrence of relapse with susceptible bacilli in patients with extensive disease, due to better sterilizing activity while maintaining the same treatment duration. Total absence of relapse with AFB smear at 2 weeks negative or scanty would suggest that shortening of the regimen to 4 months could be tried for fast converters.

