2. STUDY DESIGN

2.1 General study design

This study is a randomised clinical trial. Consecutively diagnosed smear-positive pulmonary TB patients, which conform to all of the inclusion and none of the exclusion criteria and provide informed consent, will be randomized to the intervention or control arm.

The control arm will receive the standard pulmonary TB treatment regimens recommended by the International Union against Tuberculosis and Lung Disease (The Union). This consists of:

Treatment:

New cases: 2HRZE/4HR, i.e. 2 months of isoniazid, rifampicin, pyrazinamide and ethambutol intensive phase, followed by 4 months continuation phase isoniazid plus rifampicin) (Cat. 1 regimen, 6 months)

Retreatment cases: 2 months of SHRZE (S= streptomycin) followed by 1 month of HRZE and 5 months HRE (Cat. 2 regimen, 8 months)

Any patients with *MDR TB detected* at any time will be switched to 4KHPtoGCEZ/5GCEZ, i.e. 4 months of kanamycin, isoniazid, prothionamide, gatifloxacin high-dose, clofazimine, ethambutol and pyrazinamide, followed by 5 months of gatifloxacin high-dose, clofazimine, ethambutol and pyrazinamide (MDR regimen, 9 months)

Testing:

Monitoring by smear and rapid DST as per National TB Programme (NTP) indications:

- Smears for AFB [by Ziehl-Neelsen brightfield (ZN) or auramine fluorescence (FM) technique] at diagnosis, after 2, 5 and 6 months (Cat. 1) or after 3, 5 and 8 months (Cat. 2); repeat after month 3, respectively 4, if AFB were seen at month 2 or 3
- Vital staining fluorescein diacetate (FDA) smears for AFB to confirm a positive ZN or FM result during Cat. 1
- rapid DST if fever is still present after 2 weeks, or in case an AFB smear (auramine and/or FDA) is positive during Cat. 1, or from the 3rd month of Cat. 2 onwards. Rapid DST is performed also from any retreatment case (relapse, return after default and other previously treated for at least 1 month), and from previously untreated contacts of MDR-TB

Additionally, patients enrolled in the study (control as well as intervention arm) will be followed-up for relapse 12 months after the end of treatment by clinical examination, sputum smear and slow solid culture.

The intervention consists of the standard care as provided to the control arm with the following modifications:

Treatment:

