#### Testing:

Monitoring by smear and rapid DST as per National TB Programme (NTP) indications:

- Smears for AFB [by Ziehl-Neelsen brightfield (ZN) or auramine fluorescence (FM) technique] at diagnosis, after 2, 5 and 6 months (Cat. 1) or after 3, 5 and 8 months (Cat. 2); repeat after month 3, respectively 4, if AFB were seen at month 2 or 3
- Vital staining fluorescein diacetate (FDA) smears for AFB to confirm a positive ZN or FM result during Cat. 1
- rapid DST if fever is still present after 2 weeks, or in case an AFB smear (auramine and/or FDA) is positive during Cat. 1, or from the 3rd month of Cat. 2 onwards. Rapid DST is performed also from any retreatment case (relapse, return after default and other previously treated for at least 1 month), and from previously untreated contacts of MDR-TB

Additionally, patients enrolled in the study (control as well as intervention arm) will be followed-up for relapse 12 months after the end of treatment by clinical examination, sputum smear and slow solid culture.

The intervention consists of the standard care as provided to the control arm with the following modifications:

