## **7. Analysis of secondary objectives**

7.1. To assess whether the study regimen also cures low-level rifampicin resistant TB

The interaction between treatment differences and initial rifampicin resistance mutations detected will be tested in the logistic regression model from the main analysis. Initial rifampicin resistance mutations detected is categorized as:

- None
- Low-level
- High

7.2. To assess the effectiveness of FDA vital staining screening at two weeks of treatment for early switch of non-responding rifampicin resistant TB to MDR-TB treatment, versus clinical evaluation based on fever

The proportions of initial rifampicin resistant cases started on MDR treatment within the first 2 months of primo-treatment as well as the proportion of initially present resistance never switched to the MDR regimen and not cured will be compared between the two arms using the chi-squared or Fisher's exact test.

7.3. To assess the negative predictive value of conversion at 2 weeks for relapse

The complement of the Negative Predictive value (with 95% Wilson CI) of conversion in the intervention arm will be estimated as the % of relapses among those who are already completely negative on AFB smear (auramine or FDA) at week 2.

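### The month-2 rapid-DST trigger is given as three conflicting rules, and SAP 7.2 does not say whether the MDR starts it prompts count in the week-2 FDA-versus-fever comparison

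*Protocol*

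**What the plan says.** The rule for rapid DST at month 2 appears in several places.

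- Protocol 5.3, month-2 visit (V4): "Refer for rapid DST if AFB-positive (auramine and FDA) and clinically poor evolution; switch to MDR treatment if rifampicin resistant". The smear at that visit is listed as "Cat. 1: sputum smear for AFB".
- Protocol 2.1, Testing: rapid DST "in case an AFB smear (auramine and/or FDA) is positive during Cat. 1, or from the 3rd month of Cat. 2 onwards". SAP 2.1 repeats the Cat. 1 condition: "in case an AFB smear (auramine and/or FDA) is positive during Cat. 1".
- Protocol 1.1, describing programme indications: "rapid DST in case a smear is positive at 3, 5 or 6 months".
- Protocol 5.1, schedule: the DST-referral and FDA rows are empty at month 2. The footnote "If smear-positive at this time = standard indication of the NTP, controls as well as intervention arm" is attached to months 3, 5 and 6/8 only.
- Synopsis, Follow-up: "Referral of positives for rapid rifampicin DST from 2nd or 3rd month onwards".
- Protocol 5.4: follow-up after the week-2 tests is meant to be alike in both arms, by auramine smear at 2/3 months, after which patients may be referred again.

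The endpoint affected belongs to secondary objective 2. SAP 7.2 compares by arm "The proportions of initial rifampicin resistant cases started on MDR treatment within the first 2 months of primo-treatment", and also the proportion of initially resistant patients who are never moved to the MDR regimen and are not cured.

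**The concern.** Objective 2 asks whether FDA staining at week 2 brings resistant patients to MDR treatment earlier than a fever check at week 2. A switch prompted by the month-2 smear is the work of neither test. Whether such a switch happens depends on which of the conflicting rules a clinic follows. Whether it is counted depends on how the 2-month cut-off is read, because the cut-off coincides with V4.

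Two features could act differently by arm. One rule requires a judgement of clinical evolution, which the text does not define, by staff who know the allocation. And intervention retreatment cases follow Cat. 1 and so have a month-2 smear, whereas control retreatment cases on Cat. 2 may not.

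**Working it through.** **Month-2 referral, Cat. 1, rules side by side**

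1. Any positive smear, either stain, no clinical condition: Protocol 2.1 and SAP 2.1. The Synopsis wording is compatible with this.
2. Positive on auramine and FDA, plus poor clinical evolution: Protocol 5.3, V4. This needs an FDA result. Protocol 2.1 provides FDA to confirm a positive smear during Cat. 1, but the schedule plans no FDA at month 2.
3. No month-2 referral: Protocol 1.1 (months 3, 5 and 6) and the schedule in 5.1, which agree with each other.

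A patient positive on auramine, negative on FDA and doing well is referred at month 2 under rule 1 but not under rules 2 or 3. A patient positive on both and doing badly is referred under rules 1 and 2 but not under rule 3. The rules therefore cannot all be followed.

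**Month-2 smear, Cat. 2 controls**

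- Protocol 2.1 and SAP 2.1: Cat. 2 smears at months 3, 5 and 8. Protocol 5.3 limits the V4 smear to Cat. 1 and gives every Cat. 2 patient a month-3 smear.
- Protocol 5.1: month-2 smear marked without restriction, and month 3 only for those positive at month 2.

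These also conflict.

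**Size of the comparison**

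Protocol 8.4 expects about 20 rifampicin-resistant cases, 10 per arm. This is reproduced by taking the 2% MDR figure among new cases in 2010 (Protocol 1.1): 0.02 × 1000 = 20, and 20 / 2 = 10. One patient is then 1/10 = 10 percentage points. Two-sided Fisher's exact test at 10 versus 10 shows the sensitivity: 3/10 versus 9/10 gives p = 0.020, and 4/10 versus 9/10 gives p = 0.057. One control patient counted in or out crosses 0.05.

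**Direction of the effect (assumed inputs, not in the documents)**

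Let s be the share of resistant cases caught at week 2, m the share of those missed who are smear-positive at month 2, and q the share of these who are referred, switched and counted. The counted proportion is s + (1 − s)mq. With the same m and q in both arms, the difference is (s_int − s_ctl)(1 − mq).

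Take s_ctl = 0.30, s_int = 0.60 and m from 0.5 to 0.9.

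- q = 0: difference 0.60 − 0.30 = 0.30.
- q = 1, m = 0.5: 0.80 − 0.65 = 0.15.
- q = 1, m = 0.9: 0.96 − 0.93 = 0.03.

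So a rule shared by both arms shrinks the contrast. In the retreatment stratum, if controls had no month-2 smear and still entered the endpoint, the difference at q = 1 would instead be 0.80 − 0.30 = 0.50 (m = 0.5) to 0.96 − 0.30 = 0.66 (m = 0.9). That is inflation, but only among the few resistant retreatment cases who enter.

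**The case against.** A reader might infer that the FDA-versus-fever comparison is confounded. The documents do not support that. Allocation is randomised, with separate lists for new and retreatment cases, and blocked for balance within sites (Protocol 4.4). For new cases one month-2 rule, however unclear, covers both arms. If fever misses more resistance at week 2, later catch-up helps the control arm, which is dilution and not false credit to FDA.

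A reader might also infer that a month-2 switch cannot occur among retreatment controls. The schedule marks a month-2 smear for everyone, so this is another conflict and not an established absence. The asymmetry is narrow in any case. Retreatment cases are referred for rapid DST before entry and resistant ones are ineligible; those called susceptible or with no result enter (Protocol 5.3). It is also unclear that Cat. 2 controls belong in the endpoint, since Protocol 1.1 uses primo-treatment for Cat. 1.

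Four further points have weight:

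- V4 comes after 2 months of treatment and no DST turnaround time is given, so the number of V4-prompted starts inside the window could be zero.
- A Cat. 1 patient positive at month 2 has a repeat smear at month 3, so a missed month-2 referral need not mean a long delay.
- The interim analysis (SAP 5) looks at week-2 referral directly in the first 500 patients, including resistance missed by arm.
- The Annex II algorithm is not shown in the public copy and may state one rule. That clinics act differently is therefore an inference.

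These points limit the consequences but do not remove the contradiction. Even if Annex II states a single rule, the conflicting text would still need correcting, and the interim analysis does not define the 2-month window in SAP 7.2.

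**Conclusion.** The point holds as a contradiction to be reconciled and an endpoint to be clarified. There are three distinct month-2 referral rules for Cat. 1, and two conflicting statements of the month-2 smear for Cat. 2 controls. They govern who is tested and switched, so this is more than loose wording.

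For objective 2, the week-2 contrast may be diluted by starts that neither week-2 test prompted. Scope for bias by arm is limited to the open-label judgement of clinical evolution and the few resistant retreatment cases who enter. The firm figure is 10 percentage points per patient, resting on the Protocol's expected 10 resistant cases per arm. The Fisher results and the dilution range are illustrations; the dilution range rests on assumed detection rates. This is a secondary objective of a pilot estimation study, so the change should be made, but the primary comparison does not hang on it. No view is taken on which clinical rule is right.

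**What to change.** **Protocol.** Reconcile the Synopsis, 1.1, 2.1, 5.1, 5.3 and 5.4, together with SAP 2.1 and Annex II if it differs, into one month-2 smear and referral rule. The clinical team chooses the rule, including what applies to Cat. 2 controls.

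**SAP 7.2.** Keep the prespecified proportion. Add two definitions: whether MDR starts prompted at V4 fall inside the 2-month window, and whether Cat. 2 controls are included. Then report, by arm and by new/retreatment stratum, the proportion of initially resistant cases switched after a referral made at the week-2 visit (V2), separately from switches triggered at V4 or later.

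**Cost.** Wording changes in the places listed, through the amendment route in Protocol 11.2, and one more small table. The table needs the visit that triggered each referral to be recorded. The downside is that fewer switches will be attributed to the week-2 tests.
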